8.2.4 Relationship to Investigational Product and Relationship to Study Procedures

The Investigator must assess the causal relationship between the exposure to the IP (THS or CIG) and each of the reported AEs, using the classification system and the criteria described below. The same assessment must be made separately to assess the causal relationship between the study procedures and each of the reported AEs:

Not related: The temporal relationship of the adverse event to IP administration or study procedure(s) makes a causal relationship unlikely, or concomitant medication, therapeutic interventions, or underlying conditions provide a sufficient explanation for the observed event.

Related: The temporal relationship of the adverse event to IP or study procedure(s) makes a causal relationship possible, and concomitant medication, therapeutic interventions, or underlying conditions do not provide a sufficient explanation for the observed event.

8.2.5 Expectedness

Any AE assessed as related to the IP (THS or CIG) will be assessed for its expectedness. An AE will be regarded as “unexpected” if its nature or severity is not consistent with information already recorded in Section [6.7](#) of the current Investigator’s Brochure [\[6\]](#).

8.2.6 Follow-up of Non-serious and Serious Adverse Events

Any non-serious AE that is ongoing at the time of Discharge or early termination will be followed-up by the Investigator during the Safety follow-up (SFU) period until it has been resolved, stabilized (i.e., no worsening of the condition), or an acceptable explanation has been found (e.g., a chronic condition). The follow-up of the ongoing non-serious AEs will be done via a phone call performed at the end of the SFU period. If the subject does not respond at the first phone call, two additional attempts will be made, then subject will be declared lost to follow-up.

At the end of the 3-day SFU period, all ongoing non-serious AEs will have the outcome documented as “unknown” and will not be followed-up by the Investigator. At the discretion of the Investigator, the subject will be referred to his General Practitioner to have his/her ongoing AEs addressed accordingly.

All SAEs will be followed up by the Investigator or designee after the end of the SFU period, until their resolution, stabilization (i.e., no worsening of the condition), or an acceptable explanation has been found (e.g., a chronic condition). In case the subject cannot

Confidentiality Statement

Data and information contained in this document are considered to constitute trade secrets and confidential commercial information, and the legal protections provided to such trade secrets and confidential information are hereby claimed under the provisions of applicable law. No part of this document may be publicly disclosed without the written consent of Philip Morris Products S.A.

be reached for additional information related to SAE(s), a total 3 attempts should be performed before the subject will be declared as lost to follow-up.

8.3 Reporting Serious Adverse Events

Any SAE observed during the period of collection in this study must be reported **within 24 hours of first awareness to Sponsor**, via email, having the SAE form attached.

Follow-up information should be reported on a new SAE report form, marked as a follow-up report and submitted to Sponsor according to the same timelines as described above. The follow-up SAE report form must include the minimum information required for form completion and only changed/new information needs to be specified. Information provided in the follow-up SAE report form supersedes any information that was initially reported.

The Investigator or designee is responsible for submitting the relevant reports of SAEs that occur during the study to the IEC, according to local regulations.

8.4 Reporting of Other Abnormal Findings

The other abnormal findings discovered during different clinical assessments (e.g., ECG, spirometry, vital signs, body weight) should be evaluated for the clinical significance by the Investigator/designee based on his/her medical judgement. All abnormal clinically significant test results or clinical examination findings can, at the discretion of the Investigator, be reported as AEs and handled according to the directions from Section 8.2.

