6.4 Blinding

This is an open-label study. Therefore, the subjects, the Investigator, the PMP and CRO personnel will be unblinded to the subject's sequence and product use.

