7.4 Clinical Assessments

Any clinically relevant medical condition detected during Screening visit assessments will be documented as a concomitant disease. This also applies to clinically relevant findings in laboratory values, vital signs, at spirometry and ECGs detected during Screening visit assessments. Any untoward medical occurrence in a subject detected during the study that was not present at the Screening visit must be documented as an Adverse Event (AE). Worsening of a pre-existing condition from Screening visit onwards will also be documented as an AE.

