## 8.9 Clinical Laboratory Tests (Serum Chemistry, Hematology, and Urinalysis)

Clinical laboratory evaluations (clinical chemistry, hematology, and urinalysis) will be performed at Screening, Admission (Day -1), and at the time of discharge (Day 3) or as early termination assessments, as applicable.

Out-of-normal range flags will be recorded as follows: high (H) and low (L) for numerical results and did-not-match (\*) for categorical results. If a value fails the reference range, it will automatically be compared to a computer clinically significant (CS) range. If the value falls within the computer CS range, it will be noted as "N" for not clinically significant. If the value fails (i.e., fall outside of the CS range) the computer CS range, it will be flagged with a

Philip Morris Products S.A.  
THS Induction device and regular or menthol sticks, P1-PK-12  
[REDACTED] CA39924

---

"Y" which prompts the PI to determine how the out-of-range value should be followed using 4 Investigator flags: "N", not clinically significant, "R", requesting a recheck, "^", checking at the next scheduled visit, or "Y", clinically significant. To distinguish the PI flag from the computer CS range flags, the PI flags of "N" and "Y" will be presented as "-" and "+", respectively, in the data listing. Additionally, a derived flag based on a search of the PI comments for a comment of "CS" or "Clinically Significant" will be used. The derived flag will be populated with "+" if the positive clinically significant determination is found in the comments for cases when the PI flag is populated with a "^" or a "R".

Out-of-range values and corresponding recheck results will be listed. CTCAE laboratory grading (version 5.0) will be included as well. Other lab results within this panel and time point will also be listed for this subject. Results that are indicated as CS by the PI will be listed in the table.

For all numeric laboratory values, descriptive statistics will be presented for each laboratory test by time point (baseline and discharge). Change from baseline will be summarized in a similar manner. Baseline is defined as the result closest and prior to the first product administration, which may include unscheduled or recheck results. This will typically be the result collected on Admission (Day -1). Post product use unscheduled events or rechecks will not be included in summaries. Similarly, early termination results will not be included in summaries.

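### Protocol 8.4 makes AE reporting optional for a finding already judged clinically significant, against the duty in 7.4, so AE incidence can be undercounted or recorded inconsistently from case to case

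*Protocol*

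**What the plan says.** Protocol 8.4 covers abnormal findings from clinical assessments and gives ECG, spirometry, vital signs and body weight as examples. It has two steps. Findings "should be evaluated for the clinical significance by the Investigator/designee based on his/her medical judgement". Then: "All abnormal clinically significant test results or clinical examination findings can, at the discretion of the Investigator, be reported as AEs". Nothing says when a significant finding may be left unreported.

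Protocol 7.4, the general section on clinical assessments, starts with conditions found at Screening, which are recorded as concomitant diseases, and adds: "This also applies to clinically relevant findings in laboratory values, vital signs, at spirometry and ECGs detected during Screening visit assessments". For later findings, any untoward occurrence "detected during the study that was not present at the Screening visit must be documented as an Adverse Event (AE"). It continues: "Worsening of a pre-existing condition from Screening visit onwards will also be documented as an AE".

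Protocol 8.1.1 accepts that an abnormal laboratory result can be an AE. It asks for medical judgement on one question: whether the finding is an AE in its own right or only an expression of a condition the subject already had. Protocol 8.2.1 makes recording of every non-serious AE compulsory and prefers one diagnosis to a list of its signs.

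Under Protocol 6.4, "the subjects, the Investigator, the PMP and CRO personnel will be unblinded to the subject's sequence and product use". AE incidence is an endpoint of the second secondary objective (Protocol 3.2). Laboratory AEs have their own planned summary (Protocol 12.5.2, SAP 8.8). For laboratory data, SAP 8.9 adds: "Results that are indicated as CS by the PI will be listed in the table".

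**The concern.** The decision on clinical significance already uses the investigator's judgement. Section 8.4 then permits a second decision, on whether the significant finding becomes an AE, and sets no test for it. An investigator can follow 8.4 to the letter, flag a new abnormality as significant, record no AE, and be in breach of 7.4.

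The AE tables count only what was reported. A finding dropped at the second step is missing from AE incidence and, if it is a laboratory finding, from the laboratory-AE summary. In the SAP shells the laboratory, vital-sign, ECG and spirometry summaries are laid out by randomized sequence, while the AE and product-event tables are laid out by product. An unreported finding therefore leaves the part of the safety output where products are set side by side. Whoever makes the second decision knows which product was used.

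**Working it through.** The documents state no figure on this point, so there is none to reproduce. The check compares the reporting rules, then looks at where an omission would show and what it could amount to.

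**1. The rules side by side, for a new abnormality judged clinically significant**

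| Section | Status of AE reporting | Room for judgement |
|---|---|---|
| 7.4 | Compulsory if new since Screening or worsened | None stated |
| 8.1.1 | AE if adverse and new, or worsened | AE, or expression of an existing condition |
| 8.2.1 | Compulsory once it is an AE | Diagnosis preferred to separate signs |
| 8.4 | Optional | Unlimited, after significance is decided |

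The compulsory sentence in 7.4 does not name test results. They are named in the sentences just before it, on Screening findings. The conflict therefore needs one linking step: that a new, clinically significant test abnormality is an untoward occurrence. Section 8.1.1 supports that step by treating an abnormal laboratory result as a possible AE.

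**2. Where an omitted finding would still be visible**

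- Laboratory: values flagged significant by the investigator are tabulated whether or not they became AEs (SAP 8.9, Table 14.3.4.4).
- ECG and spirometry: each assessment is classified for significance (SAP 8.11, 8.14), and the classification appears in the listings only (Appendices 16.2.8.8 and 16.2.8.9).
- Vital signs: neither SAP 8.10 nor Appendix 16.2.8.7 carries a significance flag.
- Neither document describes a reconciliation of these flags with the AE data.

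**3. How often a finding could arise**

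Safety laboratory, ECG and spirometry have one scheduled assessment after exposure, on Day 3 (Protocol Appendix A). Each subject's laboratory AE at that point goes to one product. With balanced sequences that is 30/3 = 10 subjects per product. Vital signs are taken before T0 on Days 2 and 3 and again later on Day 3 (Protocol 7.4.5, Table 7), so one scheduled set follows each product use. Up to 30 subjects per product can contribute there.

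**4. Size**

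One omitted subject among 30 users is 1/30 = 3.3 percentage points. Beyond that, rates have to be assumed. Let p be the true proportion with a significant new finding and r the share reported. Observed incidence is p × r, and the expected count is 30 × p × r.

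| p (assumed) | r = 1 | r = 0.75 | r = 0.5 |
|---|---|---|---|
| 5% | 1.50 (5.0%) | 1.12 (3.8%) | 0.75 (2.5%) |
| 10% | 3.00 (10.0%) | 2.25 (7.5%) | 1.50 (5.0%) |
| 20% | 6.00 (20.0%) | 4.50 (15.0%) | 3.00 (10.0%) |

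For laboratory AEs, with 10 subjects per product and p = 10%, the chance of seeing any event is 1 − 0.90^10 = 65% with full reporting and 1 − 0.95^10 = 40% with half reported.

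**The case against.** The best defence is that 8.4 only applies the judgement found elsewhere. Section 8.1.1 asks for care before a laboratory finding is called an AE, 7.4.5 to 7.4.7 leave follow-up and AE reporting to the investigator, and 8.2.1 lets a diagnosis stand for its signs. On that reading nothing is optional once a finding is an AE. This would hold if 8.4 referred to those limits. It does not: its discretion is open-ended and applies after significance is settled.

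The documents remain transparent about much of the data. Significant laboratory values are tabulated, and ECG and spirometry classifications are listed, so an omission there lowers the AE count without hiding the finding. That stands, except for vital signs.

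Four stronger readings are tempting and are not supported:

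- *AE counts will be biased between products.* Open-label discretion makes this possible, but nothing shows it. Every subject is to use all three products, and the scheduled laboratory, ECG and spirometry assessments after exposure occur once.
- *Different sites will follow different sections.* The study has one center. The inconsistency would be between cases.
- *Investigator-set normal ranges add product bias.* Nothing in 7.4.5 to 7.4.7 suggests that ranges vary by product, and a common range cannot by itself create a product difference. Laboratory values also pass automatic range checks first (SAP 8.9).
- *The number of measured parameters gives the size.* It counts opportunities and is not an effect.

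**Conclusion.** The conflict is in the current text. Section 8.4 makes optional, without a criterion, what 7.4 makes compulsory, and it goes beyond the limited judgement in 8.1.1. The conclusion rests on reading a new, clinically significant abnormality as an untoward occurrence, which 8.1.1 supports. The consequence is that AE incidence and the laboratory-AE summary can be undercounted or recorded inconsistently within the single center.

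The expected size cannot be derived from the documents. The 3.3 points per omitted subject assumes that 30 subjects use the product, and the reporting shares of 75% and 50% are illustrations only. A reader might infer that the product comparison of AEs is distorted; the documents support only that it is exposed to that risk. AE incidence is descriptive here, with no hypothesis to be tested and no significance level, and few events are likely over three days in healthy subjects. The wording should still be corrected, because the correction is simple and the count is reported as an endpoint.

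**What to change.** Reconcile 8.4 with 7.4 and 8.1.1 into one reporting rule that applies alike to all products. One form would replace the discretionary clause so that clinically significant findings *are reported as AEs unless present at Screening and not worsened, a manifestation of a pre-existing condition (8.1.1), or part of a diagnosis already reported (8.2.1)*. All three exceptions build on rules the protocol already contains.

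Add a clinical-significance flag for vital signs, matching those for ECG and spirometry. Before database lock, check every post-Screening result flagged significant (the investigator's + flag for laboratory values, the ECG and spirometry classifications, and the new vital-signs flag) against the AE dataset, and record which exception applies where there is no AE.

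The cost is one sentence, one flag and one data check. The AE count may be slightly higher.

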8.5 Reporting and Follow-Up of Pregnancies

8.5.1 Period of Collection and Follow-up

Pregnancies detected between the time of signature of the ICF and the time before first exposure to the IP will be considered a reason for screen failure. No pregnancy form will be filled in for that case, however the diagnosed pregnancy must be captured in the screen failure page of the CRF.

Any pregnancy detected after enrollment must be reported by the Investigator **to Sponsor within 24 hours of first awareness**. This also includes pregnancies spontaneously reported to the Investigator after the end of the study for a subject. A dedicated pregnancy form will be used to report reportable cases of pregnancy.

Any pregnancy that was potentially associated with exposure to IP (THS and CIG) will be followed-up until an outcome is reached (e.g., normal delivery, spontaneous abortion, or voluntary termination), and until 8 weeks after delivery. Any pregnancy complication, adverse pregnancy outcome or maternal complications will be recorded as an AE accordingly.

Confidentiality Statement

Data and information contained in this document are considered to constitute trade secrets and confidential commercial information, and the legal protections provided to such trade secrets and confidential information are hereby claimed under the provisions of applicable law. No part of this document may be publicly disclosed without the written consent of Philip Morris Products S.A.

The procedure outlined in Section 8.3 should be followed to collect pregnancy reports and provide any additional/follow-up information to Sponsor.

8.5.2 Reporting of Pregnancies

The Investigator is responsible for informing the responsible IEC of any pregnancy case that was reported during the study, as determined by local regulations.

8.6 Adverse Events Leading to Discontinuation

Subjects who are discontinued from the study because of an AE will undergo the Early termination (Section 9.6), as soon as practical after discontinuation and will enter the 3-day SFU period.

Any AEs or SAEs that are ongoing at the end of the SFU period will be managed as described in Section 8.2.6.

8.7 Device Malfunction, Product Complaints and Misuse

Any occurrence of a test product (THS) device malfunction, product complaints, or misuse (use not in accordance with its instructions) by a subject will be documented by the PI. Information regarding any test product (THS) events should be actively collected during the study and assessed for severity as Minor or Major:

Minor – Can be resolved easily.

Major – Cannot be resolved.

Any occurrences of a test product (THS) device malfunction (e.g., holder does not charge when inserted into the charger), product complains (e.g., stick filter fall off) or misuse by a subject (e.g., use not in accordance with its label and instructions), will be documented by the PI or designee using a device issue log, and recorded.

Any test product misuse may result in use-related hazards (Section 2.3.3).

Furthermore, any malfunction or misuse of the test product (THS) that leads to an AE/SAE will follow the same processes as described above.

Confidentiality Statement

Data and information contained in this document are considered to constitute trade secrets and confidential commercial information, and the legal protections provided to such trade secrets and confidential information are hereby claimed under the provisions of applicable law. No part of this document may be publicly disclosed without the written consent of Philip Morris Products S.A.

9 Study Activities

A detailed schedule of assessments can be found in [Appendix A](#). Measurements not conducted at the exact timepoint but conducted within the given time window (if applicable) do not constitute a protocol deviation but an accepted variability for the given timepoint.

In general, if no start time for the procedures is provided, then the procedure can be performed at any time during the day.

The main objective for this study is the evaluation of the plasma concentration-time profile of nicotine and derived PK parameters. Therefore, the collection of blood samples for determination of plasma nicotine concentration should be as close to the schedule time as possible and should take precedence over any other assessments required at the same time.

9.1 Screening Visit (Day -28 to Day -2)

The Screening visit will be performed ≤ 27 days prior to potential randomization at Baseline Day -1. First, the Informed consent form (ICF) along with study information will be given to the subject. Prior to being asked to sign the consent form, subjects will be given time to review the study information and ask any questions. When/if the ICF is signed and dated and timed, the screening procedures ([Table 3](#)) can be performed in the order deemed most practical. While it is recommended to complete as many screening procedures as possible in one day, it is permissible to complete those over more than one day. Smoking is allowed at the Screening visit.

If the inclusion and exclusion criteria are satisfactorily met after Screening visit (including negative pregnancy test for female), the site staff will call the subject to arrange the Baseline visit (Day -1) to the site.

Table 3 Time Schedule – Screening Visit

| Time | Procedures | Additional Information |
|------------------------------------|---|-----------------------------|
| Prior to any other study procedure | Informed consent process and signature of ICF | |
| During the Visit | Information on smoking risks, advice on smoking cessation | Incl. THS briefing |
| | Demographics | |
| | Medical History | Incl. concomitant diseases |
| | Concomitant medication | Incl. during ≤ 4 weeks |
| | Body weight and height | BMI |
| | FTND questionnaire | Nicotine dependence |
| | TNP Use History questionnaire | Smoking history |

Confidentiality Statement

Data and information contained in this document are considered to constitute trade secrets and confidential commercial information, and the legal protections provided to such trade secrets and confidential information are hereby claimed under the provisions of applicable law. No part of this document may be publicly disclosed without the written consent of Philip Morris Products S.A.

| Physical examination | |
|-------------------------------------|---|
| Vital signs | ≥5 min supine rest ≥15 min TNP abstinence |
| ECG | ≥10 min supine rest |
| Spirometry | ≥15 min sitting rest ≥1 hr TNP abstinence |
| Serology | HBV, HCV, and HIV |
| Venous blood sample | 
 - Safety panel (hematology and clinical chemistry) |
| Spot urine sample | 
 - Safety panel - Drug test - Cotinine test - Pregnancy test (female) |
| Alcohol breath test | |
| THS demonstration | Without product use |
| Identification of current CIG brand | Explain CIG provision for confinement period by subject |
| AE/SAE recording | |
| Review of eligibility criteria | Incl. subject's willingness to comply with study procedures, particularly periods of TNP abstinence |

Abbreviations:

AE = Adverse event; BMI = Body mass index; ECG = electrocardiogram; CIG = combustible cigarette; HBV = hepatitis B virus; HCV = hepatitis C virus; HIV = human immunodeficiency virus; hr = hour; ICF = informed consent form; Incl. = including; min = minute; SAE = Serious adverse event; THS = tobacco heating system; TNP = tobacco and/or nicotine containing product.

